14.0 STATISTICAL CONSIDERATIONS

Phase I

For the phase I portion of the study, we will employ the modified continual reassessment method (CRM) to determine the maximum tolerated dose (Faries, 1994; Goodman et al., 1995)^{61,62}. Dose-limiting toxicity (DLT) will be as defined under 13.0 and, occurring within the first 21 days after transplant. Dose cohorts of size three will be utilized and we will target the 25th percentile of the tolerance distribution, i.e., the dose level producing DLT in 25% of the patient population. Briefly, the modified-CRM design utilizes a one-parameter, logistic regression model for the dose-toxicity curve

$$p(x) = \frac{\exp(3 + \beta x)}{1 + \exp(3 + \beta x)}, \quad (1)$$

where $p(x)$ is the probability of DLT at dose level x . A prior distribution is assumed for the parameter β and the first three patients are assigned to the lowest dose level. After outcomes are observed for these patients, the posterior distribution for β is calculated and the estimated toxicity probabilities are updated. The next cohort of patients are assigned to the dose level closest to the targeted percentile, with the restriction that doses can not be escalated more than one level at a time. Enrollment is continued until a predetermined total number of patients have been studied, whereupon the MTD is derived based on the final, estimated dose-toxicity curve.

In our trial, the first cohort of three patients will be enrolled at dose level 0 and after all three of these patients have been followed to day 60 the observed number of DLTs will be used to update the posterior distribution and determine the dose level for the succeeding cohort. Since we anticipate an accrual rate of approximately three patients per month, it is likely that all three patients from a given cohort will not have been followed to 60 days before the next eligible patient becomes available. In this case we will assign such patients (termed *excess* patients) to the current dose level; once the original three patients pass the 60-day landmark, we will update the prediction probabilities using all available data. However, so as not to bias the procedure, if *excess* patients have not been followed for a full 60 days, we will not include their toxicity outcomes in the updated analysis, even if a DLT has been observed. A total of 30 patients will be enrolled in the phase I trial.

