Because delayed VOD (day 30 and day 60) of moderate severity has been observed in two of the 12 initial patients on study, the observation period for successive patients will be extended to 60 days before dose escalation. This will lead to accrual of a higher number of patients per dose level and therefore we anticipate up to 50 patients in the phase I trial.

Addendum June 2006: Pharmacokinetics for the initial 20 patients was performed in the cancer center core facility at UC. For logistical reasons and for more intensive monitoring another laboratory will be

used and technical modifications in sampling have been introduced. Therefore accrual will resume at dose level 0. This will result in accrual of an additional 20 patients to the protocol.

Phase II

The primary endpoint for the phase II portion of the trial is the disease-free survival rate (DFS) at one year defined as the proportion of patients alive and without evidence of recurrence one year after the initiation of therapy. All patients will be followed for a minimum of one year and we will test the null hypothesis that the DFS rate at twelve months is $\leq 25\%$ versus the alternative that it is at least 40%. A Simon (1989), optimal two-stage design will be employed in which 29 patients are enrolled in the first stage.⁶³ (Patients treated at the MT D during the phase I portion of the study will be included in the phase II trial.) If the number alive and without evidence of recurrence at twelve months is 7 or fewer, the study will be terminated for lack of efficacy. Otherwise, subject to the monitoring described below for graft failure, liver toxicity, and GVHD, an additional 43 patients will be enrolled for a total of 72. If 22 or fewer patients are disease free at 12 months the regimen will be rejected, whereas if 23 or more of the total 72 patients ($> 32\%$) are disease free, the regimen will be considered worthy of further evaluation in phase III trials. This design has an α -level of 10% and a power of 90% under the alternative hypothesis that the true 12-month DFS rate is 40%. The probability of early termination when the 12-month DFS rate is 25% is 0.56. However, to avoid a long suspension of the trial, accrual will continue into the second stage while the one-year outcomes in the 29 first stage patients are being accumulated.

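### DLTs already seen in excess patients are held out of the CRM update until day 60, and phase I states no rule for acting on them during the wait

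*Combined protocol and SAP*

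**What the plan says.** Section 14.0 (Phase I) describes a modified CRM in which "Dose cohorts of size three will be utilized" and "we will target the 25th percentile of the tolerance distribution". After each update, "doses can not be escalated more than one level at a time". The first update waits until all three patients of the cohort have reached day 60. Patients who arrive in the meantime are assigned "to the current dose level; once the original three patients pass the 60-day landmark", the probabilities are updated from all available data. One exception is made, "so as not to bias the procedure": if an excess patient has not completed 60 days, "we will not include their toxicity outcomes in the updated analysis, even if a DLT has been observed".

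Two time windows appear in the same section. A DLT is an event "occurring within the first 21 days after transplant". After delayed VOD was seen in two of the first 12 patients, "the observation period for successive patients will be extended to 60 days before dose escalation".

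Section 13.0 makes DLTs serious events: any fatal toxicity, grade 4 toxicity apart from hematologic and infectious events, and severe VOD.

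**The concern.** The rule sets aside information the trial already holds when it decides whether to escalate. A DLT needs no further follow-up to be known, yet it does not count until that patient reaches day 60. In addition, no refit takes place between landmarks, so patients keep going to a level whatever has happened there since the last update. At stake are patients treated above the MTD while evidence against the level is already on file.

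The stated reason, avoiding bias, is only partly a reason for this rule. Counting early DLTs while dropping event-free patients still under observation would overstate toxicity. Weighting event-free patients by the follow-up they have completed removes that distortion without withholding any DLT. If the 21-day DLT window applies, an excess patient past day 21 has a complete outcome and is still left out.

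**Working it through.** The plan states no operating characteristics for phase I, so there is no figure to reproduce.

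**1. Size of the omitted group.** Inputs: a wait of 60 days (about two months); accrual of three per month (14.0, Phase I) or four to five per month (14.0, Estimated duration of accrual).
- 3 × 2 = 6 (about 5 to 6 in practice); 4 × 2 = 8; 5 × 2 = 10.
- If patients are transplanted in order of entry, every excess patient has less follow-up than the third original patient. None has 60 days when that patient does, so the whole current group is omitted.
- Past day 21 at the landmark are those transplanted in the first 60 − 21 = 39 days. With even spacing of 10, 7.5 or 6 days, that is 3 of 6, 5 of 8 or 6 of 10.

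**2. How often this bites.** With true DLT rate p:
- At least one DLT among 6 excess patients, 1 − (1 − p)^6: 82% at p = 0.25, 95% at p = 0.40.
- 0/3 in the original three and at least one DLT in 3 excess patients past day 21, (1 − p)^3 × [1 − (1 − p)^3]: 0.422 × 0.578 = 24% at 0.25; 0.216 × 0.784 = 17% at 0.40.
- The same with at least two DLTs, (1 − p)^3 × [3p²(1 − p) + p³]: 0.422 × 0.156 = 6.6%; 0.216 × 0.352 = 7.6%.

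**3. One decision.** The printed model is logit p = 3 + βx. The plan gives neither the prior nor the dose coding. Assumed: three prior DLT curves (2%, 5% or 10% at level 0) crossed with three priors on β (exponential with mean 1; lognormal with log-SD 0.5 or 1.34), giving nine settings.
- At level 0 with 0/3 in the original three, the plan moves to level 1 in 9 of 9 (estimated rate at level 0: 0.04 to 0.08), whatever the excess patients show.
- Counting three excess patients past day 21, with follow-up weights for those without an event: one DLT keeps level 0 in 6 of 9, so this case depends on the prior; two DLTs keep it in 9 of 9 (estimate 0.30 to 0.42).

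**4. Whole trials.** Four simulations with assumed priors and different assumed true DLT curves (250 to 600 trials per setting): 50 patients, three per month, half of DLTs by day 21. One used an exponential prior with mean 1 and prior DLT rates of 5/10/17/25/35/45%. Ranges of the mean number of patients above the true MTD, plan versus a follow-up-weighted refit before each assignment that may only hold or lower the level:

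| True MTD | Plan | With refit | Reduction |
|---|---|---|---|
| Level 0 | 10.4–13.6 | 5.6–7.9 | 42% (13.6 to 7.9) to 52% (12.3 to 5.9) |
| Level 1 | 10.3–12.4 | 6.6–8.0 | 35% (12.4 to 8.0) to 40% (12.4 to 7.5) |
| Level 2 | 9.3–11.1 | 6.4–7.6 | 31% (9.3 to 6.4) to 38% (10.4 to 6.5) |

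- Under the plan, 27 to 60% of escalations were made with at least one known DLT uncounted.
- Timing of DLTs: with 20% or 80% by day 21 in place of half, an example setting went from 11.0 to 7.9 or from 11.0 to 6.1.
- Total DLTs per trial: 14.5 to 13.5, 12.1 to 11.0 and 10.5 to 9.6 for MTD at levels 0, 1 and 2.
- MTD at level 4: patients above it go from 2.7 to 1.8.
- Correct selection, plan/refit, in two of the simulations: level 0, 0.86/0.84 and 0.87/0.86; level 1, 0.71/0.71 and 0.64/0.70; level 2, 0.60/0.66 and 0.60/0.58. The standard error of a difference near 0.65 is about √(2 × 0.65 × 0.35/400) = 0.034 with 400 trials and 0.043 with 250, so all of these lie within two standard errors.

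**5. Which part of the change does the work.** Patients above the MTD for MTD at level 0 / 1 / 2, in one of the simulations:
- plan: 13.6 / 12.4 / 10.4
- follow-up weighting at scheduled updates only: 12.9 / 11.1 / 9.4
- hold-or-lower refit with immature excess outcomes still withheld: 8.8 / 8.4 / 7.6
- both: 7.9 / 7.5 / 6.5

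The refit alone gives 4.8/5.7 = 84%, 4.0/4.9 = 82% and 2.8/3.9 = 72% of the full gain.

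**The case against.** A reader might infer that these outcomes are discarded. The documents do not support that. The update uses all available data apart from immature excess patients, and the next update comes at least 60 days later. Each excess patient therefore misses one update and counts afterwards. What remains is that the decision a DLT could have stopped has by then been taken.

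A reader might also infer that nothing can act during the wait. That is too strong. Inpatients are reviewed weekly (15.1). Unexpected serious toxicity goes at once to the Study Chairman and on to the Surveillance Committee, and non-relapse deaths go to the IRB (17.0). A monitoring committee can recommend stopping (14.0). None of these routes carries a phase I DLT threshold, however. The numerical boundaries stand in the phase II part and cover graft failure, liver toxicity and GVHD, and regimen-related toxicity is classed as expected and reported only regularly (17.0).

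Three further objections stand in part. A rule that can only hold or lower will mechanically reduce exposure above the MTD, and total DLTs fall by only about one. Most of the gain comes from refitting during the wait, not from deleting the quoted clause. The June 2006 addendum restarts at level 0 with 20 additional patients. If that adds to the 50, with the initial 20 already treated, 50 + 20 − 20 = 50 new patients remain, as simulated. If only 20 remain, the gain is much smaller: 4.0 to 2.2 patients above the MTD (level 0), 1.1 to 0.9 (level 1) and none at level 2 or above.

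**Conclusion.** The concern holds in this form: known DLTs in excess patients are deferred past the decision they bear on, and phase I has no stated rule for responding to them during the 60-day wait. With 50 patients at three per month, the alternative reduces patients above the MTD by roughly 30 to 50% when the MTD is at levels 0 to 2, and by about one patient when it is at level 4. There is no reliable evidence of better or worse MTD selection.

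These sizes rest on assumed priors, dose-toxicity curves and DLT timing, none of which the plan supplies. The direction was the same across the settings tried. This is a moderate point and a cheap improvement. It does not show the design to be unsafe as it stands, and it does not reach the level of a mandatory change.

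**What to change.** First reconcile the DLT window: section 14.0 gives 21 days for the definition and 60 days for observation, and the follow-up weight depends on which applies. Also reconcile the CRM with the up-and-down rule in Appendix A (18.1.1), and the two phase I accrual rates in 14.0. State the prior and the dose coding.

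Then replace the exclusion clause along these lines: escalation is considered only at the 60-day landmark. Before each new assignment and at each scheduled update, the same CRM is refitted to all patients, with observed DLTs counted in full and event-free patients weighted by the fraction of the DLT window completed. Between landmarks this fit may hold or lower the level but not raise it. Deleting the clause without adding the refit would give only a small part of the benefit.

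Cost: one paragraph, more frequent model fits, slightly slower escalation (highest level reached about 0.2 lower on average), and about one to three more patients treated below the MTD when it lies above level 0.

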APPENDIX A: TREATMENT SCHEME
APPENDIX B: GVHD CRITERIA

Version 08/11/06, 09/13/2011, 02/20/2013

Principal Investigator

[name]

CO-INVESTIGATORS

[name].

[name].

[name].

[name].

[name].

[name]., Ph.D

[name].

[name].

[name].

[name].

[name]., Ph.D.

[name]., Ph.D.

[name].

University of Illinois at Chicago

Principal Investigator:

[name]

PROTOCOL ABSTRACT

Protocol:

A phase I-II study of busulfan-fludarabine conditioning and T-cell depleted allogeneic stem cell transplantation for patients with advanced hematologic malignancies

Principal Investigator:

[name].

Patient Eligibility:

Diagnosis:

Phase I portion:

- Relapsed or refractory acute myelogenous or lymphoid leukemia.
- Chronic myelogenous leukemia in accelerated phase or blast-crisis.
- Recurrent or refractory malignant lymphoma or Hodgkin's disease
- Recurrent or refractory multiple myeloma.
- Chronic lymphocytic leukemia, relapsed or with poor prognostic features.
- Myeloproliferative disorder (polycythemia vera, myelofibrosis) with transformation
- Myelodysplastic syndromes with more than 5% blasts.

Phase II portion:

- AML with active disease or beyond CR2
- MDS with more than 5% blasts

Zubrod performance status 2 (See Appendix B).

Life expectancy is not severely limited by concomitant illness.

Adequate cardiac and pulmonary function. Patients with decreased LVEF or PFTS will be evaluated by cardiology or pulmonary prior to enrollment on this protocol.

Calculated creatinine clearance >50 ml/min.

Serum bilirubin 2.0 mg/dl, SGPT <3 x upper limit of normal

No evidence of chronic active hepatitis or cirrhosis. HIV-negative Patient is not pregnant Patient or guardian able to sign informed consent.

Matched sibling donor, 1 Antigen mismatched relative or matched unrelated donor.

Treatment Plan:

See appendix A

PATIENT EVALUATION:

See section 6 and section 7

Miscellaneous Information:

Objectives:

1. To establish the maximally tolerated dose (MTD) of intravenous busulfan (Busulfan®) in combination with fludarabine as conditioning regimen for transplantation with in-vivo T-cell depletion
2. To evaluate disease free and overall survival after this conditioning regimen in patients with advanced AML and MDS.
3. To evaluate potential pharmacogenomic determinants of toxicity of this regimen.
4. To evaluate potential pharmacogenomic determinants of efficacy of this regimen.

Statistics:

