5.0 BACKGROUND

5.1 *Allogeneic transplantation in advanced hematologic malignancies.*

Allogeneic transplantation has been extensively used for the treatment of advanced hematologic malignancies and results in durable remissions in approximately 30% of patients. Besides patient related factors, the outcome of transplantation depends on (1) the conditioning regimen, (2) type of donor (HLA-matched vs -mismatched or unrelated), (3) Type of GVHD prophylaxis.

5.2 *Conditioning regimens for a allogeneic transplantation. Historical and institutional results.*

Traditionally, total body irradiation or high doses of busulfan in combination with high doses of cyclophosphamide have been the mainstay for conditioning in allogeneic transplantation. But more recently reduced intensity conditioning regimens have been utilized in an attempt to reduce early regimen related toxicity.¹⁻³ Such regimens assure reliable engraftment in recipients of HLA-identical transplants, and prolonged disease free survival has been demonstrated in a proportion of patients with end-stage malignancies.

We have evaluated a combination of fludarabine and melphalan as originally pioneered by Giralt et al.¹ Using this regimen, we obtained approximately 30% disease-free survival, 30% treatment related mortality and observed a high incidence of extensive chronic GVHD. Disease free survival was obtained in approximately 20-30% of the patients.⁴ In a subsequent study, at the University of Chicago (IRB 11300 A), we have continued to use the same conditioning

regimen, but employed Campath 1H (alemtuzumab), a T-cell depleting agent, instead of methotrexate for GVHD prophylaxis.⁵ This conditioning results in excellent engraftment, much decreased toxicity, near absence of chronic GVHD and excellent initial survival. Unfortunately, recurrence rates are high in patients with advanced leukemia and lymphoma and long-term disease free survival in this patient group is likely to be in the range of 20% to 35%.⁵⁻⁷ (and manuscript submitted)

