5.4 Donor type

The outcome of allogeneic transplantation is determined to a large degree by the choice of stem cell donor. The best outcomes are obtained with the use of syngeneic donors (i.e. identical twins). Grafts from such donors are accepted without risk for graft failure or graft versus host disease.

Among siblings, the probability of being identical for all major histocompatibility (HLA) antigens is approximately 25%. Allogeneic matched (HLA-identical) siblings can be identified for approximately 20-30% of the population. Seventy percent of patients who might otherwise benefit from allogeneic hematopoietic stem cell transplantation lack a suitably matched related donor. Alternative donor sources include partially matched related donors, unrelated volunteers, and previously banked placental blood. Recipients of unrelated donor transplantation will be included in this study as they have been in all our previous studies. As in our previous studies, we will use molecular typing (DNA sequencing) of 10 relevant HLA alleles (A, B, C, DR, DQ) for determining donor/recipient matching.

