8.1 DONOR SELECTION

When possible, an HLA compatible sibling will be used as a donor. For patients who do not have an HLA-compatible sibling, an unrelated donor will be identified.

In case of unrelated donor transplantation, high resolution DNA-based HLA typing will always be performed for HLA A, B, C and DR antigens

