In addition, the incidence of graft failure, liver toxicity, and high-risk, extensive chronic GVHD at 18 months will be closely monitored and evaluated. For the primary endpoint of DFS, we will employ a Simon (1989) two-stage design. Graft failure, liver toxicity, and GVHD will be monitored at specified intervals as described below. An independent Data and Safety Monitoring Committee will be established to review the data and make recommendations regarding the continuation or discontinuation of the trial. This committee is organized by the University of Chicago Cancer Center (High risk protocol monitoring committee). Since the assumptions regarding efficacy and toxicity are the same, the related donor and unrelated donor subgroups will be combined for all analyses.

Adverse Event Monitoring

Graft failure and liver toxicity will be monitored and early termination of the trial will be considered if there is evidence that the graft failure rate is $> 10\%$ or the rate of liver toxicity is $> 15\%$. Specifically, for graft failure the data will be reviewed after successive cohorts of 10 patients have been treated and we will consider terminating the trial if 4 of the first 10, 6 of the first 20, 7 of 30, 9 of 40, 10 of 50, 12 of 60, or 13 of 70 have graft failure. For liver toxicity the trial will be stopped if 5 of the first 10, 7 of the first 20, 9 of 30, 11 of 40, 13 of 50, 15 of 60, or 17 of 70, develop liver toxicity. With regard to high-risk, extensive GVHD, we will review the data after the first 10, 20, and 30 patients with successful engraftment and without evidence of relapse reach their 18-month landmark. (By the time 30 patients have reached this point, all 72 patients will have almost surely been accrued.) Evidence that the rate of high-risk, extensive GVHD is $> 40\%$ will lead to consideration for early stopping. Specifically, if 8 of the first 10, 13 of the first 20, or 17 of 30 such patients develop GVHD at any time

prior to 18 months we will consider terminating the trial. Each of these three stopping guidelines approximates a Pocock (1977)⁶⁴ group sequential monitoring boundary for a one-sided, overall alpha level of 0.10.

Additional Statistical Analyses

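### Donor types are pooled for every analysis and donor type is left out of the Cox model, although the protocol calls it a main determinant of outcome; the permitted donors are also stated inconsistently

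*Combined protocol and SAP*

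**What the plan says.** **Pooling.** Under Phase II, section 14.0 gives equality of the efficacy and toxicity assumptions as the reason why "the related donor and unrelated donor subgroups will be combined for all analyses". It names two groups only, related and unrelated. The boundaries for graft failure, liver toxicity and GVHD are all stated for the combined patients. Under Additional Statistical Analyses no donor stratum, subgroup or covariate is named. The Cox model for progression or death takes genotype and busulfan pharmacokinetic parameters as predictors.

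**Donor type and outcome.** Section 5.4 opens with "The outcome of allogeneic transplantation is determined to a large degree by the choice of stem cell donor". Section 5.1 lists "type of donor (HLA-matched vs -mismatched or unrelated") among three determinants of outcome, beside the conditioning regimen and the GVHD prophylaxis.

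**Who may be a donor.** The abstract allows "Matched sibling donor, 1 Antigen mismatched relative or matched unrelated donor". Section 8.1 prefers an HLA-compatible sibling and otherwise turns to an unrelated donor. Section 9.1.5 (tacrolimus) and section 9.1.7 (back-up harvest) both make provision for mismatched recipients.

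**Typing.** Section 5.4 bases matching on "molecular typing (DNA sequencing) of 10 relevant HLA alleles (A, B, C, DR, DQ"). Section 8.1 says of unrelated donors that "high resolution DNA-based HLA typing will always be performed for HLA A, B, C and DR antigens".

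**The concern.** The reason given for pooling sits badly with the protocol's own background, and the rule has no exception for description. Three things follow.

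- The trial could end with one pooled 12-month disease-free survival (DFS) rate and pooled toxicity rates, from a donor mix that the plan neither fixes nor undertakes to report. A reader deciding on phase III could not tell whether the result reflects the regimen or the mix.
- The Cox model omits a baseline factor that the protocol treats as prognostic. Even if donor type is unrelated to genotype, the omission costs precision and tends to pull hazard ratios towards 1. If the two are unbalanced by chance, which is easy at this sample size, it confounds the comparison.
- It is unclear whether a mismatched relative may serve as donor and, if so, where that patient counts. By the two labels in section 14.0 the patient is related. Section 9.1.5 groups mismatched with unrelated recipients.

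**Working it through.** **1. The plan's own figures.** Inputs from section 14.0: stop if 7 or fewer of 29 are disease-free at 12 months; reject the regimen if 22 or fewer of 72 are; null rate 25%, alternative 40%.

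P(declare worthy | p) = Σ over x = 8 to 29 of b(x; 29, p) × P(Y ≥ 23 − x), with Y ~ Bin(43, p).

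- p = 0.25: 0.098 (stated alpha 10%). Probability of early termination P(X ≤ 7) = 0.557 (stated 0.56).
- p = 0.40: 0.901 (stated power 90%).

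A grid search for the optimal design at these inputs returns the same 7/29, 22/72. Nothing here is wrong.

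**2. The donor passages side by side.**

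| Place | Mismatched relative or recipient | Loci |
|---|---|---|
| Abstract | Relative admitted, one antigen | not given |
| 5.4 | Partially matched relatives listed as an alternative source | A, B, C, DR, DQ (5 × 2 = 10 alleles), as the basis for matching |
| 8.1 | Not mentioned | A, B, C, DR (4 loci) always typed for unrelated donors |
| 9.1.5, 9.1.7 | Recipients provided for | not given |
| Appendix A, 18.1.3 | No donor-specific tacrolimus provision, unlike 9.1.5 | not given |
| Appendix A, 18.1.5 | Recipients provided for | not given |
| 14.0 | Not placed in either group | not given |

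The prior institutional study described in section 5.5 used matched sibling or matched unrelated donors, so as described it would not supply a benchmark for mismatched relatives. The documents do not say where the 25% comes from.

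**3. Why the mix matters to a reader (illustration on assumed rates).** Assume that 25% and 40% are right for a 50:50 mix and that related recipients have DFS higher by a gap g. With a share w related, the pooled rate is p + g(w − 0.5).

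- No regimen benefit, w = 0.75: pooled rate 0.275, 0.2875 or 0.30 for g = 10, 15 or 20 points. P(declare worthy) = 0.21, 0.28 or 0.36.
- Full benefit, w = 0.25: pooled rate 0.375, 0.3625 or 0.35. P(declare worthy) = 0.82, 0.76 or 0.69.

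At w = 0.5 both stay at 0.098 and 0.901. The fix does not alter these probabilities, because the pooled test is kept. Reporting by donor type lets a reader see which situation applies.

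**4. What donor-specific reporting can deliver.** Approximate 90% half-width at a rate of 40%: 1.645 × √(0.4 × 0.6 / n).

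- n = 72: 9.5 points
- n = 36: 13.4 points
- n = 18: 19.0 points

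This is enough to describe, not to test.

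**5. Room for a covariate.** If all 72 patients enter the Cox model and 12-month DFS lies between 40% and 25%, there are 72 × 0.60 = 43 to 72 × 0.75 = 54 events by one year. One or two extra parameters are affordable, with less room if fewer patients have samples. For veno-occlusive disease (VOD), a rate at the plan's 15% liver-toxicity limit would give 72 × 0.15 ≈ 11 events, so adjustment there depends on the count.

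**The case against.** Pooling is a conventional choice for a single-arm trial of 72 patients, and section 5.4 says that unrelated recipients were in all the group's previous studies. The background sentences are general, and the one in section 5.4 leads into identical-twin donors. Section 14.0 speaks of design assumptions, not of equal biology. An independent committee reviews the data and nothing stops it from asking for donor type. Section 15.4 plans to send outcome data on unrelated recipients to the donor registry, so donor type is identifiable. All of this stands. It supports keeping the pooled primary test; it gives no reason to withhold donor-specific description.

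A reader might infer four stronger things that the documents do not support.

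- *That the pooling rule bars donor type as a covariate.* It does not, since a covariate model is fitted to the combined sample. Donor type is absent because the list of Cox predictors leaves it out.
- *That section 8.1 defines a match, so that a donor differing only at DQ is matched there and mismatched under 5.4.* Section 8.1 sets a minimum of loci to type; only section 5.4 gives a basis for matching. The gap is that DQ belongs to that basis but is not among the loci always typed.
- *That the stopping boundaries are defective because a high rate in one donor group can be diluted.* The graft-failure boundary is crossed with probability 0.058 at a uniform 10%. It is crossed equally often under an assumed 25% in one quarter of patients and 5% in the rest, which also averages 10%. That is how a limit on the overall rate should behave, and the fix leaves it unchanged.
- *That the different tacrolimus duration shows that the groups differ.* It appears in section 9.1.5 but not in Appendix A, so it is itself a point to reconcile.

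**Conclusion.** The point holds as a gap in analysis and reporting, together with an eligibility inconsistency. Three things rest on the text alone: equality of assumptions is asserted without data and against sections 5.1 and 5.4; the pooling rule, taken literally, excludes donor-specific rates; and the Cox model omits a factor that the protocol itself calls prognostic. The abstract and section 8.1 differ on who may be a donor, and section 14.0 leaves the mismatched relative unplaced.

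No stated alpha, power or decision threshold is wrong. The size of any distortion cannot be derived from the documents. The donor-mix figures above rest on an assumed gap of 10 to 20 points, an assumed share of related donors, and rates calibrated to a 50:50 mix. They show why composition should be reported and are not estimates for this trial. The change is worth making because it is cheap and because the phase III decision rests on the pooled rates.

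**What to change.** 1. In section 14.0, restrict the pooling rule to the Simon test and the stopping boundaries, and state the basis for assuming equal rates. Leave the test and the boundaries as they are.
2. Add donor type (matched related, mismatched related, unrelated; collapsed if sparse) as a covariate in the Cox model and, where event numbers allow, in the VOD model. State in which group a mismatched relative counts.
3. Report 12-month DFS, graft failure, liver toxicity and GVHD by donor type with 90% intervals, labelled descriptive, and show the same tables at committee reviews.
4. Reconcile the abstract and sections 5.4, 8.1, 9.1.5, 9.1.7 and Appendix A on permitted donor types, typed loci and donor-specific provisions. Which rule is right is for the investigators.

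The cost is a few lines of text, tables from data already collected, and one or two model parameters. The donor-specific intervals will be wide and must not be read as tests.
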